### 3.2.3 Exploratory Endpoints

1. Reduction in size of liver and spleen, as visualized by ultrasound.
2. Reduction in number of cutaneous lesions, as determined by SCORMA and photography.
3. Assessment of metabolic bone disease and bone turnover as determined by the peripheral blood markers, bone-specific alkaline phosphatase, osteocalcin, N-terminal propeptide of type I procollagen, and crosslinked telopeptides of type I collagen.
4. Frequency and severity of AEs during the open-label treatment period.

## 4 Study Population

### 4.1 Recruitment Plan

All participants will be recruited from the NIAID study 02-I-0277, "Regulation of the Proliferation and Survival of Normal and Neoplastic Human Mast Cells." Participants will also be screened on that study.

**Recruitment of NIH staff:** NIH staff, NIH contractors, NIH fellows and members of their immediate families may participate in this protocol. We will follow the Guidelines for the Inclusion of Employees in NIH Research Studies and will give each employee a copy of the "NIH Information Sheet on Employee Research Participation."

For NIH staff members:

- NIH staff may be a vulnerable class of participants.
- Neither participation nor refusal to participate will have an effect, either beneficial or adverse, on the participant's employment or work situation.
- The employee participant's privacy and confidentiality will be preserved in accordance with NIH CC and NIAID policies, which define the scope and limitations of the protections.
- For NIH staff participants, consent will be obtained by an individual independent of the staff member's team. Those in a supervisory position to any staff member and co-workers of the staff member will not obtain consent.
- The importance of maintaining confidentiality when obtaining potentially sensitive and private information from co-workers or subordinates will be reviewed with the study staff at least annually and more often if warranted.

## 4.2 Participant Inclusion Criteria

Participants must meet all of the following criteria to be enrolled in this study:

1. Male or female participant  $\geq 18$  and  $< 75$  years of age at screening.
2. Enrolled on NIAID protocol 02-I-0277.
3. Documented pathologic diagnosis of ISM.
4. MC-QoL score of at least 25% (which suggests participant is at least somewhat affected by all McQoL questions).
5. Willing and able to undergo a bone marrow biopsy and aspirate.
6. Absolute neutrophil count (ANC)  $\geq 2000/\mu\text{L}$ .
7. Hemoglobin  $\geq 12.0$  g/dL (males),  $\geq 11$  g/dL (females).
8. Platelet count  $\geq 150,000/\mu\text{L}$ .
9. Alanine transaminase (ALT) and aspartate transaminase (AST)  $< 1.5$  times the upper limit of normal (ULN).
10. Willing to allow storage of blood and bone marrow for future use in medical research.
11. Willing to allow genetic testing on biospecimens.
12. Able to provide informed consent.
13. Participants who can become pregnant must agree to use adequate contraception when engaging in sexual activities that can result in pregnancy. Adequate contraception must be used consistently, beginning at least 1 month before the beginning of dosing and lasting until 3 months after the final dose of study drug. Acceptable methods of contraception include the following:
  - Hormonal contraception (non-oral only).
  - Male or female condom with spermicide.
  - Diaphragm or cervical cap with a spermicide.

- Intrauterine device.

### 4.3 Participant Exclusion Criteria

Individuals meeting any of the following criteria will be excluded from study participation:

1. Any abnormality that would be scored as a Grade 4 toxicity on the Common Terminology Criteria for Adverse Events (CTCAE) version 5.0. Only clinically significant lab results will deem the subject ineligible
2. Infected with HIV or has other known immunodeficiency.
3. Has an active infection, including localized infection.
4. Active diverticulitis.
5. Active or chronic viral hepatitis.
6. Active or latent tuberculosis.
7. Use of any other anti-IL-6 or anti-IL-6R agent within 1 year prior to the date informed consent was obtained.
8. Use of cytoreductive therapy for mastocytosis within 1 year prior to the date informed consent was obtained.
9. Known lymphoma or advanced and metastatic solid tumors on active therapy (including chemotherapy) within 1 year prior to the date informed consent was obtained.
10. Use of chemotherapy within 1 year prior to the date informed consent was obtained.
11. Receipt of any marketed (eg, omalizumab) or investigational biologic or monoclonal antibody reported to affect mast cell activation within 5 half-lives prior to date informed consent was obtained.
12. Receipt of intravenous (IV) immunoglobulin within 30 days prior to the date informed consent was obtained.
13. Receipt of live attenuated vaccines within 30 days prior to the date informed consent was obtained.
14. History of alcohol or drug/abuse within 12 months prior to date informed consent was obtained.
15. Is allergic to any component of the sarilumab formulation.
16. Pregnant or breastfeeding.
17. Any condition that, in the opinion of the investigator, contraindicates participation in this study.

**Co-enrollment guidelines:** Co-enrollment in other trials is restricted, other than enrollment on observational studies. Study staff should be notified of co-enrollment as it may require the approval of the investigator.

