## Protocol Summary

Full Title:	A Phase 2 Randomized Double-Blinded Placebo-Controlled Study to Evaluate the Safety and Efficacy of Subcutaneous Sarilumab in Improving the Quality of Life in Subjects with Indolent Systemic Mastocytosis
Short Title:	Sarilumab for Treatment of ISM
Clinical Phase:	2
IND Sponsor:	OCRPRO/DCR/NIAID/NIH
Conducted by:	LAD/NIAID
PI:	[name]
Sample Size:	N = 30
Accrual Ceiling:	N = 60
Study Population:	Participants will be aged 18 to 74 years-old who have been diagnosed with indolent systemic mastocytosis (ISM).
Accrual Period:	5 years
Study Design:	This will be a randomized, placebo-controlled double-blinded study. Thirty participants will be randomized (1:1) to receive 8 subcutaneous (SC) injections of 200 mg of sarilumab (trade name Kevzara) or placebo once every 2 weeks (Q2W) for 16 weeks. Participants will be evaluated at each study visit for improvement of symptoms of ISM and safety. Study visits for dose 4, 6, and 8 of study agent administration may be self administered at home without study assessments. After a 12-week washout period, all participants will be offered the opportunity to continue 200-mg sarilumab SC Q2W for 52 more weeks, with regular safety checkups.
Study Duration:	Start Date: October 2018 End Date: July 2027 Participants will be on study for up to 91 weeks, from screening through the end of the 1-year for open-label administration.
Study Agent/ Intervention Description:	Kevzara (sarilumab, Sanofi/Genzyme [Cambridge, MA. USA]), 200 mg/dose or placebo via SC injection Q2W for 16 weeks

(8 doses), with the option to continue sarilumab at 200 mg Q2W for 52 more weeks.

- Primary Objective:** To determine the efficacy and safety of 8 doses of sarilumab in improving the quality of life (QoL) in participants with ISM.
- Secondary Objectives:**
1. To assess the need for symptomatic relief with standard medicines.
  2. To assess the effect of sarilumab on serum tryptase.
  3. To investigate the effect of sarilumab on the allelic frequency of D816V *KIT* in peripheral blood.
  4. To investigate the effects of sarilumab on bone marrow mast cell infiltrates.
- Exploratory Objectives:**
1. To assess the effect of sarilumab on end-organ targets of mastocytosis.
  2. To evaluate the effect of sarilumab on skin manifestations.
  3. To evaluate the effect of sarilumab on markers of bone marrow resorption and deposition.

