#### 5.3 Randomization and Blinding/Unblinding Procedures

Eligible participants will be allocated 1:1 to study agent or placebo. A randomization scheme will be generated by the study statistician who will provide a randomized list of arm assignments to the NIH CC Pharmacy. A permuted block approach, with varying block sizes, will be used for the randomization process.

The participants, the investigators, and all who are involved in the evaluation of the study participants including study monitors and central laboratory personnel are blinded to a participant's treatment assignment until all participants have completed the week 16 visit. The NIH research pharmacist is identified as the unblinded third party who will be in charge of treatment assignment, maintaining study supplies/inventory list, and preparing the blinded study medication for each participant. The NIH research pharmacist will be independent of any study assessments. To maintain blinding, any discussion of the treatment assignment between the clinicians and the pharmacy staff is prohibited until the study is unblinded. Unblinding will occur when the final participant completes their week 28 visit (section 6.2.5), or in the case of early termination or study drug discontinuation, after the participant's final study visit.

Participants will be assigned a screening number after completion of the protocol consent for enrollment in the study in the Clinical Research Information Management System of the NIAID (CRIMSON). The study statistician will generate the randomization codes. These codes will be maintained by the NIH research pharmacist. A study allocation number (1, 2, etc) will be assigned when the participant is ready to be randomized. Randomization is defined as the time that the pharmacy is notified that this new participant, with this study allocation number, is being enrolled. This should coincide with the day that the first dose of study drug is administered. Randomization will continue until there are 30 participants who initiate study drug and have at least the first post-baseline QoL measurement at 4 weeks. Note that participants who do not meet these criteria still remain in the study, and attempts to obtain subsequent QoL measures should be made.

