## 5.7 Prohibited Medications and Procedures

Participants may not receive any live vaccine while they are being treated with sarilumab because inhibition of IL-6 may obstruct the normal immune response.

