## **6.1 Screening (Days –60 to –2)**

Informed consent will be obtained before the following screening tests are conducted:

1. Physical exam with vital signs, including height and weight.
2. Medical history/medication overview.
3. Assessment of ISM symptoms.
4. Blood draw for clinical evaluations:
  - a. Complete blood count with differential (CBC/diff).
  - b. Acute care, hepatic, and mineral panels.
  - c. Serum tryptase.
  - d. Prothrombin/partial thromboplastin time (PT/PTT).
  - e. HIV test (anti-HIV-1/2 antibodies).
  - f. Hepatitis B and C antibody test, B DNA, and C RNA.
  - g. QuantiFERON Gold tuberculosis test.
5. Serum or urine pregnancy test (participants of childbearing potential only).
6. MC-QoL.
7. SCORMA.
8. MSAS.

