## **6.2 Randomized, Double-Blinded, Placebo-Controlled Treatment Period**

### **6.2.1 Baseline (Days –2 to 0)**

After eligibility has been confirmed, participants will visit the NIH CC for baseline testing. Participants may be admitted as inpatients and will be randomized to receive sarilumab or placebo. The following procedures will then be done at baseline:

1. Physical exam with vital signs.
2. Overview of medical/medication history.
3. Assessment of baseline symptoms of ISM.

4. Assessment of AEs.
5. Blood draw for clinical evaluations:
  - a. CBC/diff.
  - b. Acute care, hepatic, and mineral panels.
  - c. PT/PTT.
  - d. Total protein.
  - e. Lipid panel.
  - f. Serum tryptase.
  - g. C-reactive protein (CRP).
6. Urine or serum pregnancy test (for participants of childbearing potential only).
7. Blood draw for DNA and RNA collection.
8. Collection of serum (8 mL serum separator tube [SST]) for storage.
9. Serum IL-6 levels.
10. Serum markers of bone marrow resorption and deposition.
11. Plasma for storage (10 mL green top tube [GTT]).
12. Whole blood for storage (3 mL lavender top tube [LTT]).
13. MC-QoL.
14. SCORMA.
15. MSAS.
16. MQLQ/MSAF.
17. *KIT* D816V mutation analysis on blood.
18. Flow cytometry on blood.
19. Photography of affected areas (optional).
20. Skin punch biopsy (optional).

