14. MQLQ/MSAF
15. KIT D816V mutation analysis on blood.
16. Flow cytometry on blood.
17. Photography of affected areas.
18. Diary review.

At the end of this visit, participants who continue to meet all eligibility criteria (sections 4.2 and 4.3) will be offered the opportunity to continue on sarilumab for another 52 weeks. Prior to beginning the open-label treatment, a safety assessment of any AEs that may have occurred during the randomized treatment period will be reviewed with the participant. Participants who decline will end their participation after this visit. Those who accept will continue on the study as described below (section 6.3).

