### **6.3 Optional Open-label Treatment Period**

For the optional open-label portion of the study, participants will receive 200-mg sarilumab SC Q2W for 52 weeks (26 doses). Participants will be trained by the study team to self-administer the injection at home. The first dose will be given following the post-treatment visit (section 6.2.5), which will be considered week 1 for this portion of the study. Therefore, the final dose will be administered on week 51. The participant will be provided with a memory aid (Appendix I), in addition to the side effect/medication change diary, to keep track of self-administered doses of sarilumab.

For this first dose, the participant will be monitored during administration and for 1 hour after to observe for any immediate drug-related AEs. Participants will be discharged after postdose monitoring if they have not experienced any serious hypersensitivity reactions. Hypersensitivity reactions will be treated as clinically appropriate.

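### A live vaccine given between consent and the first dose is stopped only by investigator discretion, because exclusion 13 counts back from consent and section 5.7 starts with treatment

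*Combined protocol and SAP*

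**What the plan says.** Two rules in the protocol deal with live vaccines.

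- **Entry, section 4.3, exclusion 13:** "Receipt of live attenuated vaccines within 30 days prior to the date informed consent was obtained". The window ends on the consent date.
- **On study, section 5.7:** "Participants may not receive any live vaccine while they are being treated with sarilumab". The reason given is that blocking IL-6 may impair the immune response.

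The timing comes from four other places.

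- **Section 6.1 (Days -60 to -2):** "Informed consent will be obtained before the following screening tests are conducted". Consent can therefore fall about 60 days before dosing.
- **Section 6.2.1 (Days -2 to 0):** "After eligibility has been confirmed, participants will visit the NIH CC for baseline testing". Medication history is taken again at this visit, but no re-check of the section 4.3 windows is stated.
- **Section 5.3:** randomization is the moment the pharmacy is notified, and "This should coincide with the day that the first dose of study drug is administered".
- **Sections 6.2.5 and 6.3, open label:** "participants who continue to meet all eligibility criteria (sections 4.2 and 4.3) will be offered the opportunity to continue on sarilumab", and "The first dose will be given following the post-treatment visit". The Protocol Summary calls the preceding 12 weeks a washout.

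The general controls are the recording of concomitant medications (5.6), the investigator's right to refuse entry for any contraindicating condition (exclusion 17) and the investigator's right to pause dosing for any safety issue (12.6). None of them names vaccines or an interval.

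**The concern.** The reason given in 5.7 concerns exposure to the drug, so the interval that matters runs from vaccine to dose. Exclusion 13 measures the interval from vaccine to consent. When consent is early, the rule turns away the more distant vaccination and is silent on the closer one.

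Elsewhere the protocol ties pre-dose safeguards to dosing. Contraception must begin at least a month before dosing (4.2), breastfeeding must have stopped before treatment begins (4.4), and a negative pregnancy test is needed before the first dose (6.2.2). The vaccine rule is out of step with these.

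What is at stake is the safety of a participant who has a live vaccine shortly before dose 1 and is then allocated to sarilumab. The primary analysis, the type I error rate and the power are untouched.

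**Working it through.** The plan gives no figure to reproduce. The check is a day count on the stated windows.

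**Inputs**

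- Consent is c days before dose 1, with c from 2 to about 60 (6.1; dose 1 is Day 0 in 6.2.2).
- Exclusion 13 looks back 30 days from consent (4.3).
- The bar in 5.7 cannot start before Day 0.
- Assumption: the 30 days in exclusion 13 is also the intended interval before dosing. The documents state no vaccine-to-dose interval.

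**Step 1. Days covered by neither rule.** Exclusion 13 covers Day -(c + 30) to Day -c, and 5.7 begins on Day 0. For c = 60, Days -59 to -1 fall under neither rule, which is 59 whole days.

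**Step 2. How much of that gap lies in the last 30 days before dosing.** Uncovered days = min(c, 30).

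| Consent | Exclusion 13 covers | Uncovered, of the 30 days before dose 1 |
|---|---|---|
| Day -2 | Day -32 to Day -2 | 2 |
| Day -14 | Day -44 to Day -14 | 14 |
| Day -30 | Day -60 to Day -30 | 30 |
| Day -60 | Day -90 to Day -60 | 30 |

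This counts elapsed days from consent to dose. Counting only whole calendar days strictly between the two gives c - 1 for short gaps, so consent on Day -2 leaves Day -1 alone.

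**Step 3. An example.** With consent on Day -60, a vaccine on Day -75 lies inside Day -90 to Day -60 and excludes. A vaccine on Day -3 is after consent and before treatment, so neither vaccine rule reaches it.

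**Step 4. Whether another control fills the gap.** Section 6.2.1 places eligibility confirmation before the baseline visit and mentions randomization before listing the medication history. The medication change diary is first handed out on Day 0 (6.2.2). Section 5.6 records use without restricting it. Exclusion 17 and section 12.6 depend on judgement.

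**Step 5. Open label.** Week 16 to week 28 is (28 - 16) × 7 = 84 days, or 77 to 91 with the ± 7-day window. All 30 days before the first open-label dose therefore fall off drug, outside a literal reading of 5.7. Protection then rests on how the eligibility re-check in 6.2.5 is read.

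**The case against.** The strongest reply is that no participant is wholly unguarded. Exclusion 17 is itself a stated rule. Medication history is repeated at baseline, and randomization should fall on the dosing day. An investigator who learns of a Day -3 vaccine can refuse entry, and 12.6 allows a pause. In the blinded period, harm also needs a vaccine in a short window, a missed or disregarded history, and allocation to sarilumab (about 15 of 30 participants). All of this stands and limits the weight of the point. It does not supply an interval, and it leaves a safety rule to the diligence of whoever takes the history.

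Three stronger readings are tempting, and the documents do not support them.

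- **That every consent-anchored exclusion is a safety gap.** Exclusions 7 to 12 and 14 use the same anchor, but nothing in the documents shows a harm from it. For a 1-year window, the uncovered part is 2/365 to 60/365, or 0.5% to 16.4%, with no stated consequence.
- **That open-label entry is unprotected.** Section 6.2.5 asks that participants still meet all criteria. A re-check of windows fixed to the original consent could never change its answer, so the natural reading is that they are re-run at week 28. What remains is that the text does not name the new anchor.
- **That 30 days before dosing is an established safe interval.** It is borrowed from exclusion 13.

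**Conclusion.** The point holds for live vaccines before dose 1. The entry rule has the wrong anchor, and between consent and Day 0 only discretionary controls apply. On the assumption that 30 days is the intended interval, up to min(c, 30) of the days before dosing are uncovered, which is all 30 whenever consent is on Day -30 or earlier. The 59-day figure for consent on Day -60 does not need that assumption.

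For open label the point is only one of clarity. The documents give no rate of live vaccination, so the number of participants affected cannot be estimated and may be very small. This is a safety wording amendment worth making because it is specific and cheap. No efficacy or power claim follows from it.

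**What to change.** 1. **Section 4.3, exclusion 13:** count the 30 days back from the first dose of study agent.
2. **Section 5.7:** run the live-vaccine bar from consent to the end of treatment, including weeks 16 to 28 for those planning open label.
3. **Section 6.2.1:** confirm the vaccine interval from the medication history already taken there, asking about vaccines by name, before the pharmacy is notified.
4. **Section 6.2.5, with a phrase in 6.3:** state that the 30-day vaccine window counts back from the first open-label dose, and that this dose may be postponed until the window clears. This deals with anyone vaccinated during the off-drug weeks despite item 2.

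Exclusions 7 to 12 and 14 may be re-anchored for consistency. If exclusion 11 is re-counted at week 28, blinded study agent must be expressly exempt. That criterion covers monoclonal antibodies reported to affect mast cell activation within 5 half-lives, and the Précis describes sarilumab as reducing mast cell reactivity. The last blinded dose is at week 14, so (28 - 14) × 7 = 98 days, and 98/5 = 19.6 days is the longest half-life that would clear. The documents give no half-life.

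**Cost.** No new procedure is needed. An occasional first dose is postponed: a Day -3 vaccine moves it by about 30 - 3 = 27 days. Screening tests would be repeated if they then fall outside the 60-day limit, that is, if they were done more than 60 - 27 = 33 days before the planned Day 0. A bone marrow examination done at screening would be at most 60 + 27 = 87 days old, within the 150 days that Appendix A allows. Re-anchoring also admits some people now excluded, such as the Day -75 case, whose interval has cleared by dosing.

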#### 4.4 Justification for Exclusion of Special Populations

**Exclusion of pregnant women:** It is not known whether this drug can cause fetal harm or adversely affect reproductive capacity in humans. The limited human data with this drug in pregnant women are not sufficient to inform drug-associated risk for major birth defects and miscarriage. Monoclonal antibodies are actively transported across the placenta during the third trimester of pregnancy and may affect immune response in the in utero–exposed infant. Levels of immunoglobulin G, in response to antigen challenge, may be reduced in the fetus/infant of treated mothers. Therefore, to reduce risk, pregnant participants are excluded from this study.

**Exclusion of breastfeeding women:** There is an unknown but potential risk for sarilumab to be excreted in human milk, so there is the potential risk of AEs in nursing infants. Therefore, breastfeeding must have been discontinued before treatment with sarilumab begins.

**Exclusion of children:** Mastocytosis that is diagnosed in children often resolves by 18 years of age. This drug has also not been evaluated in pediatric patients. Therefore, the risk-benefit ratio would not justify targeting this population.

